9.3 Efficacy Variables

The efficacy variables for this study are defined below:

- Quantitative determination of TUV_{joint} and TUV_{global}
- Qualitative (i.e., visual) determination of tilmanocept localization in planar and SPECT/CT images of the bilateral hands and wrists;
- Quantitative determination of tilmanocept localization in planar and SPECT/CT images of the bilateral hands and wrists.

It is presumed that the presence of radiotracer uptake for a joint indicates the presence of activated macrophages. The use of the term "localization" is synonymous with radiotracer uptake.

The efficacy endpoints for this study, by arm, are as follows:

Primary Endpoint(s)

ARM 1

• The normal limits of TUV_{joint} (on a per joint basis) in HC subjects, which are defined as the 5 and 95 percentiles of TUV_{joint} of bilateral joints (i.e., bilateral wrists, metacarpophalangeal joint [MCPs], proximal interphalangeal [PIPs]). The normal range will be determined separately for each of the three blinded readers.

ARM 2

• The qualitative evaluations of SPECT/CT in detecting localization within synovial spaces of the bilateral hands and wrists in HCs and RA subjects.

Secondary Endpoints

ARM 1

• Applicability of the Normal (Gaussian) distribution to TUV_{joint} data.

ARM 2

- Quantitative evaluations of Tc 99m tilmanocept localization from SPECT/CT within synovial spaces of the bilateral hands and wrists in HCs and RA subjects.
- Normative joint-specific SUV.
- Predictive value of planar scans for SPECT/CT scans.

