9.5.3 Analysis of Efficacy Variables

All efficacy analyses will be conducted on both the ITD and PP populations. The ITD population will be the primary analysis set.

9.5.3.1 Primary Endpoint Arm 1

The distribution of TUV_{joint} in HC subjects will be summarized with descriptive statistics: mean, standard deviation, n, minimum, maximum, and median per reader, joint, and view. The 5 and 95 percentiles will be estimated with quantile regression fitting an intercept as a fixed term. The lower and upper limits of normal TUV_{joint} will be determined using non-parametric confidence intervals and kernel density-based confidence intervals.

9.5.3.2 Primary Endpoint Arm 2

Localization of tilmanocept in the hands and wrists will be summarized with frequency counts and percentages by reader and joint.

9.5.3.3 Secondary Endpoint Arm 1

Normal quantile plots will be provided per joint and reader, along with the *p*-value for the Shapiro-Wilk test of Normality.

9.5.3.4 Secondary Endpoints Arm 2

SUV will be calculated and summarized on both a per-joint and a total of all joints with summary statistics: mean, standard deviation, n, minimum, maximum, and median.

The predictive value of planar scans for SPECT/CT qualitative findings will be summarized per joint and reader with a crosstabulation and the uncertainty coefficients for row | column, column | row, and symmetric. The planar result will be deemed "positive" (i.e., inflamed) if $TUV_{joint} > 95$ percentile of the reader results for the same joint in Arm 1. Otherwise, the planar result will be deemed "negative".

Additional efficacy analyses may be described in the NAV3-35 Statistical Analysis Plan (SAP).

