#### 2.2 Analysis Populations

The following analysis populations will be used in the study:

**Safety Population** – The safety population includes all patients that have been enrolled in the study and injected with Tc 99m tilmanocept.

**Intent-to-Diagnose (ITD) Population** – The ITD population includes all subjects that have been enrolled in the study, injected with Tc 99m tilmanocept, and

received all imaging and evaluations necessary for the primary endpoint(s) appropriate to their respective arm.

**Per Protocol (PP) Population:** The PP population will include all ITD subjects without major protocol violations. All protocol violations will be classified as major or minor prior to database lock.

All efficacy analyses will be carried out on the ITD and PP populations with the ITD population being the primary analysis set. All analyses of safety data and baseline subject characteristics will be carried out on the safety population. A data listing displaying the patients excluded from each population will be created, as shown in Appendix B.

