#### Arm 2:

The qualitative evaluations of planar and SPECT/CT in detecting localization within synovial spaces of the bilateral hands and wrists in HCs and RA subjects.

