# 7.0 List of Analysis Tables, Figures and Listings

Table No.	Table Title	Included in Final Tables	Shown in Appendix B
1	Subject Disposition by Study Arm	X	X
2	Demographics and Baseline Data Summary Statistics by Arm – Continuous Variables (Safety Population)	Х	Х
3	Demographics and Baseline Data Summary Statistics by Arm – Categorical Variables (Safety Population)	Х	Х
4	Summary of Study Drug Administration by Arm (Safety Population)	Х	Х
5	Summary of TUV joint on both Arms Per Reader, Joint, and View (ITD population)	Х	Х
6	Summary of TUV joint on both Arms Per Reader, Joint, and View (PP Population)	Х	
7	Summary of SUV on Arm 2 per Joint and a Total of All Joints (ITD population)	Х	Х
8	Summary of SUV on Arm 2 per Joint and a Total of All Joints (PP Population)	Х	
9	Normal Range of TUV joint for the Three Blinded Readers in All Arm 1 and 2 Healthy Control Subjects (ITD Population)	Х	Х
10	Normal Range of TUV joint for the Three Blinded Readers in All Arm 1 and 2 Healthy Control Subjects (PP Population)	Х	
11	Correlation Between TUV joint and Age and BMI – All Arm 1 and 2 Healthy Control Subjects (ITD Population)	Х	Х
12	Correlation Between TUV joint and Age and BMI – All Arm 1 and 2 Healthy Control Subjects (PP Population)	Х	
13	Frequency Counts and Percentage of Localization in SPECT/ CT Imaging in RA Subjects (ITD Population)	Х	Х
14	Frequency Counts and Percentage of Localization in SPECT/ CT Imaging in RA Subjects (PP Population)	Х	
15	Shapiro-Wilk P-Value for Normality Test for TUV joint Data – All Arm 1 and 2 Healthy Control Subjects (ITD Population)	Х	Х
16	Shapiro-Wilk P-Value for Normality Test for TUV joint Data – All Arm 1 and 2 Healthy Control Subjects (PP Population)	Х	
17	Predictive Value of Planar Scans for SPECT/CT Per Joint and Reader (ITD Population)	Х	Х
18	Predictive Value of Planar Scans for SPECT/CT Per Joint and Reader (PP Population)	Х	
19	Number and Percentage of Subjects with TEAEs (Safety Population)	Х	Х
20	Summary of TEAEs (Safety Population)	Х	Х
21	Number and Percentage of Subjects with TESAEs (Safety Population)	Х	Х
22	Number and Percentage of Subjects With TEAEs by Severity Grade (Safety Population)	Х	Х
23	Number and Percentage of Subjects With TEAEs by Level of Relationship to Tc 99m Tilmanocept (Safety Population)	Х	Х
24	Number and Percentage of Subjects With TEAEs by Level of Relationship to Procedure (Safety Population)	Х	

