#### Headers

The table number will be on the first line of the title. The title area will contain the Sponsor name, the study number, and the name of the table. The title area will contain the page number (Page x of y) on the far right, 1 line above the name of the table.

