## **Table Disclaimer**

The format of the mock tables shown in the appendix of this SAP will be the format of the deliverable tables to the extent that Word document constructed tables can match production tables produced by SAS. This formatting includes the content and format of the header and footer areas of the tables. The Sponsor agrees to the format of the tables as shown in the appendix.

Further programming charges will be applicable for changes in the format of tables (including title statements, notes, data dependent footnotes, etc.) made after the approval of the SAP.

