# Table format is repeated for the PP population

<sup>a P-value testing H0: Correlation Coefficient = 0 vs H1: Correlation Coefficient ≠ 0. STATKING Clinical Services (DD-MMM-YYYY) Source Program: xxxxxxx.sas

Page x of y

Table 13. Frequency Counts and Percentage of Localization in SPECT/CT Imaging in RA Subjects
Navidea Biopharmaceuticals - Study No. NAV3-35

ITD Population (N=xxx)

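### The Arm 2 primary-endpoint tables (13 and 14) cover RA subjects only, so SPECT/CT localization in the five Arm 2 healthy controls is not directly summarized

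*SAP*

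**What the plan says.** Protocol 9.3 defines the Arm 2 primary endpoint as "The qualitative evaluations of SPECT/CT in detecting localization within synovial spaces of the bilateral hands and wrists in HCs and RA subjects". SAP 4.1.1 keeps the same two groups but adds planar imaging: "The qualitative evaluations of planar and SPECT/CT in detecting localization within synovial spaces of the bilateral hands and wrists in HCs and RA subjects".

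The analysis text in Protocol 9.5.3.2 is one sentence, repeated in SAP 4.2.1: "Localization of tilmanocept in the hands and wrists will be summarized with frequency counts and percentages by reader and joint". It does not restrict the summary to RA subjects.

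In SAP 7.0, the only frequency tables for this endpoint are Table 13 (ITD) and Table 14 (PP), and both titles end with a restriction to RA subjects. The Table 13 shell in SAP Appendix B repeats it: "Frequency Counts and Percentage of Localization in SPECT/CT Imaging in RA Subjects". Its columns are joint, reader, no, yes and total. There is no arm column and no HC-2 block, and Table 14 reuses the same format.

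SAP Appendix A treats the table name as part of the title area ("The title area will contain the Sponsor name, the study number, and the name of the table") and counts header content as part of the agreed deliverable: "This formatting includes the content and format of the header and footer areas of the tables".

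Protocol 3.1.2.3 says why the Arm 2 HCs are enrolled: they supply control data against which the RA subjects can be compared.

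**The concern.** The endpoint and its analysis text name one population, and the tables that report it name a smaller one. A programmer who follows the shells produces a primary Arm 2 summary without the HCs.

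In a feasibility study of whether SPECT/CT shows localization in inflamed joints, an RA percentage means little without the corresponding percentage in uninflamed joints. High localization in RA with none in controls, and high localization in both, would lead to opposite conclusions. Tables 13 and 14 would look the same in either case.

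A slip in one title is possible, but the RA-only assumption occurs a second time. Footnote b of the Data Listing 22 shell states that SPECT/CT is performed only in the RA part of Arm 2. That conflicts with Protocol Table 4, Protocol 8.4.1.2, the schedule of events, SAP 1.1 and 1.2, and the HC-2 rows of the Table 7 shell.

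**Working it through.** The plan states no figure for this point, so the check sets the passages side by side, followed by simple counts.

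**Who is in the endpoint and who is in the table**

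| Place | Subjects covered |
|---|---|
| Protocol 9.3 and SAP 4.1.1, Arm 2 primary endpoint | HC and RA |
| Protocol 9.5.3.2 and SAP 4.2.1, analysis text | No restriction |
| SAP 7.0, Tables 13 and 14 | RA only |
| SAP Appendix B, Table 13 shell | RA only, no group column |

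The ITD definition does not explain the gap. SAP 2.2 admits subjects who "received all imaging and evaluations necessary for the primary endpoint(s) appropriate to their respective arm". An Arm 2 HC with the required SPECT/CT is therefore in the ITD population, yet is absent from the ITD table for that endpoint.

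**Whether another output fills the gap**

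- *Table 7* has HC-2 and RA blocks, but reports SUV, a secondary quantitative endpoint.
- *Table 17* cross-tabulates planar against SPECT/CT results per joint and reader. It is a secondary-endpoint table with no HC/RA split. Its title is not limited to RA, so on a plain reading it pools both groups.
- *Data Listing 23* shows SPECT/CT localization by subject, and its arm footnote includes HC-2. As shelled it has no reader column, so it does not support a by-reader HC summary.

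**Size**

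Inputs: 5 HCs and 10 RA subjects in Arm 2 (Protocol 9.4, SAP 1.3), and 22 DAS28 joints in the hands and wrists (Protocol 8.4.2, SAP 1.0). That SPECT/CT is read on the same 22 joints is an assumption.

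- Subjects omitted: 5 / (5 + 10) = 33.3%.
- Joint assessments omitted per reader: 5 × 22 = 110 of 15 × 22 = 330.
- Denominators per reader and joint: if left and right are separate rows, 5 HC and 10 RA, so one HC subject is 1/5 = 20 percentage points. If sides are pooled, 5 × 2 = 10 HC joints and 10 × 2 = 20 RA joints, so one HC joint is 10 points. The shell does not say which applies.

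**Illustration, with an assumed RA result of 60% for one joint and reader**

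| HC result | Table 13 as shelled | Table 17 SPECT/CT-positive total, sides separate | Same, sides pooled |
|---|---|---|---|
| None localized | 6/10 = 60% | (6 + 0)/15 = 40.0% | (12 + 0)/30 = 40.0% |
| All localized | 6/10 = 60% | (6 + 5)/15 = 73.3% | (12 + 10)/30 = 73.3% |

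With sides pooled, the Table 13 entry is 12/20, again 60% in both rows. The HC count can be recovered only by subtracting Table 13 from Table 17: 6 − 6 = 0 or 11 − 6 = 5 positives, out of 15 − 10 = 5. This works only if Table 17 includes the HCs and both tables use the same subjects and reads. Table 17 also needs a planar TUV result for each joint, and no values are imputed (SAP 2.3), so its denominators may differ.

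**The case against.** The strongest reply is that this is a mislabelled shell and not a decision to drop the controls. The endpoint and analysis text name or allow both groups, and nothing says that a shell title overrides them. The Table Disclaimer in SAP Appendix A concerns format and billing, and it expressly foresees title changes after approval, at a charge. Arm 2 is descriptive, the HC scans are still acquired and listed, and five subjects give coarse percentages: for a single joint and reader, 0/5 localized has an exact 95% upper limit of 52.2%. The analysis text also asks for counts by reader and joint, not by subject group.

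Much of this stands. It is an inconsistency between text and shells, with no evidence of intent. The subtraction route is uncertain: if footnote b of Data Listing 22 were followed, Table 17 would contain no HCs and subtraction would recover nothing. Separate HC-2 and RA blocks are a recommendation, resting on the stated control role of the HCs and on the Table 7 layout, and not something the analysis text requires.

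None of it removes the mismatch. A provision that lets the title be changed does not change it, and no other listed table gives HC localization frequencies separately. Small numbers limit how firmly the HC percentages can be read. They are not a reason to leave the HCs out of a primary summary defined to include them.

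**Conclusion.** The concern holds. As shelled, Tables 13 and 14 omit one third of the planned Arm 2 subjects (5 of 15) from the only direct summary of the Arm 2 primary endpoint. That figure rests only on planned enrolment and the table titles. The 110 of 330 joint assessments per reader also assume that SPECT/CT is read on the same 22 joints, and the 60%, 40.0% and 73.3% figures are illustrative.

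No test, power or error rate is affected. The consequence is for reporting: the RA percentages would stand without their controls, and a reader would have to reconstruct the HC result from a secondary table, if that proved possible. This should be corrected before the tables are produced.

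**What to change.** Retitle Tables 13 and 14 to cover Arm 2 HC and RA subjects, both in SAP 7.0 and in the Appendix B shell. Give the shell separate HC-2 and RA blocks by joint and reader, following the layout of Table 7, and state whether left and right joints are separate rows.

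Two smaller discrepancies can be settled in the same edit:

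- Reconcile footnote b of Data Listing 22 with SAP 1.1 and 1.2 and the protocol, which give SPECT/CT to all of Arm 2.
- Reconcile the planar component in the SAP 4.1.1 endpoint with Protocol 9.3. The protocol's primary endpoint omits it, although the same section lists visual planar localization among the efficacy variables. If it stays in the endpoint, it needs a frequency table, because none is listed.

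The cost is edits to titles, one shell and a footnote, plus the reconciled endpoint wording and a further shell if planar is kept. SPECT/CT is already scheduled for every Arm 2 subject, so no new data are needed. The SAP's Table Disclaimer says that format changes after approval, titles included, carry programming charges.

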#### Localized on SPECT/CT

Joint	Reader	No	Yes	Total
xxxxxxxxxxx	xx	xxx	xxx	XXX
		XX.X%	xx.x%	
	xx	xxx	xxx	XXX
		XX.X%	xx.x%	
	xx	xxx	xxx	XXX
		xx.x%	XX.X%	

STATKING Clinical Services (DD-MMM-YYYY) Source Program: xxxxxxx.sas

Table format is repeated for the PP population.

Page x of y

Table 15. Shapiro-Wilk P-Value for Normality Test for TUVjoint Data - All Arm 1 and 2 Healthy Control Subjects

Navidea Biopharmaceuticals - Study No. NAV3-35

ITD Population (N=xxx)

Test for Normality

Test	Statistic	P-Value
Shapiro-Wilk	xxx	xxx

STATKING Clinical Services (DD-MMM-YYYY) Source Program: xxxxxxx.sas

All Table format is repeated for the PP population

Page x of y

Table 17. Predictive Value of Planar Scans for SPECT/CT Per Joint and Reader
Navidea Biopharmaceuticals - Study No. NAV3-35

ITD Population (N=xxx)

SPECT/CT (Standard of Truth)

Reader	Joint	Planar Scans	Positive	Negative	Total	Uncertainty Coefficients	Estimated 95 %tile
XX	XXX	TUVjoint > 95 (Positive)	XXX	XXX	XXX	XXX	XXX
		Negative	XXX	XXX	XXX		
		Total	XXX	xxx	XXX		
	XXX	TUVjoint > 95 (Positive)	XXX	xxx	xxx	xxx	XXX
		Negative	XXX	XXX	xxx		
		Total	XXX	XXX	XXX		
xx	xxx	TUVjoint > 95 (Positive)	xxx	XXX	xxx	xxx	xxx
		Negative	XXX	XXX	XXX		
		Total	XXX	XXX	XXX		
	xxx	TUVjoint > 95 (Positive)	xxx	XXX	XXX	XXX	XXX
		Negative	XXX	XXX	XXX		
		Total	XXX	xxx	XXX		
XX	XXX	TUVjoint > 95 (Positive)	XXX	xxx	xxx	xxx	xxx
		Negative	XXX	XXX	XXX	*****	*****
		Total	XXX	XXX	XXX		
	xxx	TUVjoint > 95 (Positive)	xxx	xxx	xxx	xxx	xxx
		Negative	XXX	XXX	XXX		
		Total	XXX	XXX	XXX		

If there are no major protocol deviations, then analysis tables for the ITD and PP populations will contain identical results. STATKING Clinical Services (DD-MMM-YYYY)
Source Program: xxxxxxx.sas

#### All Table format is repeated for the PP population

Page x of y

Table 19. Number and Percentage of Subjects with TEAEs
Navidea Biopharmaceuticals - Study No. NAV3-35
Safety Population (N= xxx)

Adverse Event Categoryb:	HC-1	HC-2	RA	Overall
Total Number of TEAEs	xxx	xxx	XXX	xxx
Subjects with at Least One TEAE	xxx (xxx%)	xxx (xxx%)	xxx (xxx%)	xxx (xxx%)
System Organ Class 1	xxx (xxx%)	xxx (xxx%)	xxx (xxx%)	xxx (xxx%)
Preferred Term 1	xxx (xxx%)	xxx (xxx%)	xxx (xxx%)	xxx (xxx%)
Preferred Term 2	xxx (xxx%)	xxx (xxx%)	xxx (xxx%)	xxx (xxx%)
System Organ Class 2	xxx (xxx%)	xxx (xxx%)	xxx (xxx%)	xxx (xxx%)
Preferred Term 1	xxx (xxx%)	xxx (xxx%)	xxx (xxx%)	xxx (xxx%)
Preferred Term 2	xxx (xxx%)	xxx (xxx%)	xxx (xxx%)	xxx (xxx%)

STATKING Clinical Services (DD-MMM-YYYY)

<sup>a HC-1 = healthy control-Arm 1, HC-2 = healthy control-Arm 2, RA = rheumatoid arthritis (stable treatment regimen; Arm 2)

b Adverse events coded with MedDRA Coding Dictionary Version XXX

Page x of y

# Table 20. Summary of TEAEs Navidea Biopharmaceuticals - Study No. NAV3-35 Safety Population (N=xxx)

		Arma		
	HC-1	HC-2	RA	Overall
Subjects With at Least One TEAE	xxx	xxx	XXX	xxx
Maximum TEAE Severity Grade				
Mild	xxx (xxx%)	xxx (xxx%)	xxx (xxx%)	xxx (xxx%)
Moderate	xxx (xxx%)	xxx (xxx%)	xxx (xxx%)	xxx (xxx%)
Severe	xxx (xxx%)	xxx (xxx%)	xxx (xxx%)	xxx (xxx%)
Highest Relationship of TEAE to Tc 99m tilmanocept				
Definitely Not [n(%)]	xxx (xxx%)	xxx (xxx%)	xxx (xxx%)	xxx (xxx%)
Probably Not [n(%)]	xxx (xxx%)	xxx (xxx%)	xxx (xxx%)	xxx (xxx%)
Possibly [n(%)]	xxx (xxx%)	xxx (xxx%)	xxx (xxx%)	xxx (xxx%)
Probably [n(%)]	xxx (xxx%)	xxx (xxx%)	xxx (xxx%)	xxx (xxx%)
Definitely [n(%)]	xxx (xxx%)	xxx (xxx%)	xxx (xxx%)	xxx (xxx%)
Highest Relationship of TEAE to Study Procedure				
Definitely Not [n(%)]	xxx (xxx%)	xxx (xxx%)	xxx (xxx%)	xxx (xxx%)
Probably Not [n(%)]	xxx (xxx%)	xxx (xxx%)	xxx (xxx%)	xxx (xxx%)
Possibly [n(%)]	xxx (xxx%)	xxx (xxx%)	xxx (xxx%)	xxx (xxx%)
Probably [n(%)]	xxx (xxx%)	xxx (xxx%)	xxx (xxx%)	xxx (xxx%)
Definitely [n(%)]	xxx (xxx%)	xxx (xxx%)	xxx (xxx%)	xxx (xxx%)
Subjects with at Least One TESAE	xxx (xxx%)	xxx (xxx%)	xxx (xxx%)	xxx (xxx%)

a HC-1 = healthy control-Arm 1, HC-2 = healthy control-Arm 2, RA = rheumatoid arthritis (stable treatment regimen; Arm 2) STATKING Clinical Services (DD-MMM-YYYY) Source Program: xxxxxxx.sas

Page x of y

Table 21. Number and Percentage of Subjects with TESAEs
Navidea Biopharmaceuticals - Study No. NAV3-35
Safety Population (N=xxx)

		Arma		
Adverse Event Categoryb:	HC-1	HC-2	RA	Overall
Total Number of TESAEs	xxx	xxx	xxx	xxx
Subjects with at Least One TESAE	xxx (xxx%)	xxx (xxx%)	xxx (xxx%)	xxx (xxx%)
System Organ Class 1	xxx (xxx%)	xxx (xxx%)	xxx (xxx%)	xxx (xxx%)
Preferred Term 1	xxx (xxx%)	xxx (xxx%)	xxx (xxx%)	xxx (xxx%)
Preferred Term 2	xxx (xxx%)	xxx (xxx%)	xxx (xxx%)	xxx (xxx%)
System Organ Class 2	xxx (xxx%)	xxx (xxx%)	xxx (xxx%)	xxx (xxx%)
Preferred Term 1	xxx (xxx%)	xxx (xxx%)	xxx (xxx%)	xxx (xxx%)
Preferred Term 2	xxx (xxx%)	xxx (xxx%)	xxx (xxx%)	xxx (xxx%)

STATKING Clinical Services (DD-MMM-YYYY)

<sup>a HC-1 = healthy control-Arm 1, HC-2 = healthy control-Arm 2, RA = rheumatoid arthritis (stable treatment regimen; Arm 2)

b Adverse events coded with MedDRA Coding Dictionary Version XXX

Page x of y

Table 22. Number and Percentage of Subjects With TEAEs by Severity Grade
Navidea Biopharmaceuticals - Study No. NAV3-35
Safety Population (N=xxx)

Part 1 of  $4 - HC-1^a$ 

	Severity Grade						
Adverse Event Categoryb:	Mild	Moderate	Severe				
Total Number of TEAEs	xxx	xxx	xxx				
Subjects with at Least One TEAE	xxx (xxx%)	xxx (xxx%)	xxx (xxx%)				
System Organ Class 1	xxx (xxx%)	xxx (xxx%)	xxx (xxx%)				
Preferred Term 1	xxx (xxx%)	xxx (xxx%)	xxx (xxx%)				
Preferred Term 2	xxx (xxx%)	xxx (xxx%)	xxx (xxx%)				
System Organ Class 2	xxx (xxx%)	xxx (xxx%)	xxx (xxx%)				
Preferred Term 1	xxx (xxx%)	xxx (xxx%)	xxx (xxx%)				
Preferred Term 2	xxx (xxx%)	xxx (xxx%)	xxx (xxx%)				

STATKING Clinical Services (DD-MMM-YYYY)

Source Program: xxxxxxx.sas

Table format repeats for HA-2, RA (Parts 2 and 3) and overall (Part 4).

<sup>a HC-1 = healthy control-Arm 1, HC-2 = healthy control-Arm 2, RA = rheumatoid arthritis (stable treatment regimen; Arm 2)

b Adverse events coded with MedDRA Coding Dictionary Version XXX

Page x of y

Table 23. Number and Percentage of Subjects With TEAEs by Level of Relationship to Tc 99m Tilmanocept

Navidea Biopharmaceuticals - Study No. NAV3-35

Safety Population (N=xxx)

Part 1 of 4 :  $HC-1^a$ 

Level of Relationship

	Definitely	Probably	Possibly	Probably	Definitely
Adverse Event Categoryb:	Not	Not	Related	Related	Related
Total Number of TEAEs	XXX	XXX	XXX	XXX	XXX
Subjects with at Least One TEAE	xxx (xxx%)				
System Organ Class 1	xxx (xxx%)				
Preferred Term 1	xxx (xxx%)				
Preferred Term 2	xxx (xxx%)				
System Organ Class 2	xxx (xxx%)				
Preferred Term 1	xxx (xxx%)				
Preferred Term 2	xxx (xxx%)				

Source Program: xxxxxxx.sas

Table format repeats for HC-2, RA (Parts 2 and 3) and overall (Part 4). Full Table (all parts) repeats for Table 24.

<sup>a HC-1 = healthy control-Arm 1, HC-2 = healthy control-Arm 2, RA = rheumatoid arthritis (stable treatment regimen; Arm 2)

b Adverse events coded with MedDRA Coding Dictionary Version XXX STATKING Clinical Services (DD-MMM-YYYY)

Page x of y

Table 25. Serum Chemistry Clinical Laboratory Parameters Summary Statistics by Arm
Navidea Biopharmaceuticals - Study No. NAV3-35
Safety Population (N=xxx)

					Std				
Parameter(units)	Arma	Visit	Data Type b	Mean	Dev	n	Min	Max	Median
xxxxxxxx (xxx)	HC-1	Screening (Baseline)	RAW	XXX	XXX	XXX	XXX	XXX	XXX
		Day 0 (Visit 2)	RAW	xxx	XXX	XXX	XXX	XXX	XXX
			CFB	XXX	XXX	XXX	XXX	XXX	XXX
	HC-2	Screening (Baseline)	RAW	XXX	XXX	XXX	XXX	XXX	XXX
		Day 0 (Visit 2)	RAW						
			CFB	XXX	XXX	XXX	XXX	XXX	XXX
	RA	Screening (Baseline)	RAW	XXX	XXX	XXX	XXX	XXX	XXX
		Day 0 (Visit 2)	RAW						
			CFB	XXX	XXX	XXX	XXX	XXX	XXX
xxxxxxxx (xxx)	HC-1	Screening (Baseline)	RAW	xxx	XXX	xxx	xxx	XXX	xxx
		Day 0 (Visit 2)	RAW	XXX	XXX	XXX	XXX	XXX	XXX
			CFB	xxx	XXX	XXX	XXX	XXX	XXX
	HC-2	Screening (Baseline)	RAW	XXX	XXX	XXX	XXX	XXX	XXX
		Day 0 (Visit 2)	RAW						
			CFB	XXX	XXX	XXX	XXX	XXX	XXX
	RA	Screening (Baseline)	RAW	XXX	XXX	XXX	XXX	XXX	XXX
		Day 0 (Visit 2)	RAW						
			CFB	xxx	XXX	XXX	XXX	XXX	XXX

Source Program: xxxxxxx.sas

Table format repeats for Tables 26 and 27.

<sup>a HC-1 = healthy control-Arm 1, HC-2 = healthy control-Arm 2, RA = rheumatoid arthritis (stable treatment regimen; Arm 2)

b RAW = data recorded in database; CFB = change from baseline= (parameter value at the current time point)-(Baseline parameter value) STATKING Clinical Services (DD-MMM-YYYY)

Page x of y

Table 28. Serum Chemistry Clinical Laboratory Parameters Shift Table by Arm
Navidea Biopharmaceuticals - Study No. NAV3-35
Safety Population (N=xxx)

Part 1 of 3: HC-1a

